3.6 Safety Assessment

Safety data will be summarised by actual treatment received (and in total for selected analyses) based on the Safety Population.

Safety and gastrointestinal tolerability will be compared between ferric maltol oral suspension and ferrous sulfate oral liquid via the incidence of TEAEs, TESAEs and TEAEs leading to premature discontinuation of study drug, estimated as the number of subjects with at least one event divided by the number of subjects in the Safety Population.

Adverse Events (AEs) will be categorised by primary system organ class and MedDRA preferred term as coded using the MedDRA dictionary version 24.0. The number, intensity, relation to study medication and action taken will be described by incidence tables. Serious Adverse Events (SAEs) will be listed and tabulated separately.

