8.7 TREATMENT COMPLIANCE

Subjects will be instructed to take the study drug as described in detail on the drug labels and by the Investigator/designee.

Subjects (ferric maltol and ferrous sulfate) will be instructed on Visit 2 to complete a dosing diary from the evening of Visit 2 until the next visit, in order to document the day and time that they took their morning and evening doses on those treatment days whilst at home. Subjects will be instructed to return all unused supplies medication packaging on their visits, having withheld their dose of ferric maltol on PK Day 2 morning. Compliance will be assessed from the dosing diary entries and reconciled using the drug accountability form.

If a subject is found to be non-compliant with the study medication (defined as less than 80% or more than 120% compliant with the dosage schedule), the subject/parent/legal guardian will be counselled and trained on the importance of maintaining adherence to study medication. If the subject is repeatedly non-adherent, a decision will be made by the medical monitor and/or Sponsor as to whether the subject should be withdrawn from the study treatment.

If the subject discontinues the study due to intolerance to either ferrous sulfate or ferric maltol, this should be documented in the eCRF.

Subjects who do not attend their visits may be withdrawn from the study. A copy of the relevant local SPC/PI for ferrous sulfate will be available in the Investigator Site File (ISF). Special safety information and warnings/precautions relating to the drug will be highlighted to the Investigator during the Site Initiation Visit (SIV).

The delivery of medication to the site, its use and return, as well as subject-specific compliance, will be reconciled and documented using a Drug Accountability Form in order to monitor compliance with the medication schedule. All opened containers, together with remaining contents, and unopened containers will be kept by the Investigator in a secure, locked area until return to the drug supplier by the monitor or destruction by the site if agreed with the Sponsor/designee. The Investigator will use the IMP only within the framework of this clinical study and in accordance with the current, approved study protocol.

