11 SAFETY

11.1 DEFINITIONS

11.1.1 ADVERSE EVENT (AE)

An AE is any untoward medical occurrence in a subject administered a pharmaceutical product and does not necessarily have a causal relationship with this treatment. An AE can therefore be any unfavourable or unintended sign or symptom, intercurrent illness, injury, or any concomitant impairment of the subject's health, temporally associated with the use of a medicinal product, whether or not considered related to the medicinal product.

A treatment-emergent AE is any AE temporally associated with the use of a study drug, whether or not considered related to the study drug.

AEs include:

- Exacerbation of a chronic or intermittent pre-existing condition/disease/symptom
 present at baseline that worsen during the study including either an increase in
 frequency and/or intensity.
- Disease or medical condition detected or diagnosed after study drug administration even though it may have been present prior to the start of the study.
- Events considered by the Investigator to be related to study-mandated procedures.
- Abnormal safety assessments, e.g. laboratory test abnormalities, physical exam findings or vital sign measurements must be reported as AEs if they represent a clinically significant finding in the medical and scientific judgment of the Investigator, symptomatic or not, which was not present at baseline or if present at baseline, worsened during the course of the study or led to dose reduction, interruption or permanent discontinuation of study drug. However, if an abnormal laboratory or other safety-related test result is associated with clinical signs or symptoms, the signs or symptoms should be recorded as an AE. If signs and symptoms are part of a diagnosis, then the diagnosis should be recorded as AE.
- Signs, symptoms of a suspected drug interaction.
- Signs, symptoms of a suspected overdose of either the study drug or a concomitant medication (overdose per se will not be reported as AE/SAE).

AEs do not include:

• Medical or surgical procedure, e.g., surgery, appendectomy, endoscopy, tooth extraction, transfusion (as these are treatments for an AE). However, the event resulting in the procedure is the AE (e.g. appendicitis, abdominal pain).

CONFIDENTIAL Page 65 of 80

- Pre-existing disease or medical condition documented at baseline that does not worsen.

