2 STUDY OVERVIEW

2.1 Study Objectives

2.1.1 Primary Objective

- To compare the safety and gastrointestinal tolerability of ferric maltol oral suspension and ferrous sulfate oral liquid in children and adolescents aged 2 years to 17 years, and assess the safety and tolerability of ferric maltol oral suspension in children 1 month to less than 2 years, in the treatment of iron deficiency anaemia during the 12 weeks treatment period.
- To assess the effect on haemoglobin (Hb) in children and adolescents aged 1 month to 17 years after twice daily ferric maltol oral suspension administration for 12 weeks.

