2.3 Study Endpoints

2.3.1 Primary Endpoints

- Safety and gastrointestinal tolerability:
 - Treatment-emergent Adverse Events (TEAE),
 - o Treatment-emergent Serious Adverse Events (TESAEs),

- Treatment-emergent Adverse Events leading to premature discontinuation of study drug/PK assessments from baseline to Week 12.
- Change in Hb concentration from baseline to Week 12.

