3.6.1 Adverse Events (AEs)

AEs will be captured from the date of informed consent through study completion (Follow-up visit). All AEs will be coded to system organ class and preferred term using MedDRA version 24.0. TEAEs are defined as AEs that start after the first dose of study drug.

An overview of AEs will be provided including counts and percentages of subjects (and event counts) with the following:

- Any AEs,
- Any TEAEs (overall and by maximum severity),
- Any study drug related TEAEs (overall and by maximum severity),
- Any SAEs,
- Any TESAEs,
- Any study drug related TESAEs,
- Any TEAEs leading to discontinuation of study drug,
- Any study drug-related TEAEs leading to discontinuation of study drug.
- Any AEs leading to death.

Counts and percentages of subjects (and event counts) will also be presented by system organ class and preferred term for each of the categories in the overview.

Listings will be presented specifically for SAEs and TEAEs leading to discontinuation of study drug.

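### The GI half of the first primary objective has no designated GI measure: the stated comparison uses all-cause adverse-event rates in a Safety Population that is not confined to the randomised children

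*SAP*

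**What the plan says.** The first primary objective in SAP 2.1.1 (and Protocol 6.1) is "To compare the safety and gastrointestinal tolerability of ferric maltol oral suspension and ferrous sulfate oral liquid" at ages 2 to 17. Infants from 1 month to under 2 years are to be assessed, not compared.

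The matching endpoint (Protocol 6.3, SAP 2.3.1) lists TEAEs, TESAEs and "Treatment-emergent Adverse Events leading to premature discontinuation of study drug/PK assessments from baseline to Week 12". None of these is specific to the GI tract.

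The comparison sentence in SAP 3.6 is "Safety and gastrointestinal tolerability will be compared between ferric maltol oral suspension and ferrous sulfate oral liquid via the incidence of TEAEs, TESAEs". Its third measure is stopping study drug early because of a TEAE, and every measure is "estimated as the number of subjects with at least one event divided by the number of subjects in the Safety Population". Protocol 12.2.1 uses the same measures and denominator.

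The definitions are all-cause. SAP 3.6.1 has "TEAEs are defined as AEs that start after the first dose of study drug", and Protocol 11.1.1 counts an event "whether or not considered related to the study drug".

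Three other provisions bear on the point:
- SAP 3.6.1 tabulates every overview category, including drug-related TEAEs and TEAEs leading to discontinuation, by system organ class and preferred term.
- SAP 3.3.1 summarises reasons for early discontinuation by treatment. Protocol 8.7 adds: "If the subject discontinues the study due to intolerance to either ferrous sulfate or ferric maltol, this should be documented in the eCRF".
- SAP 3.1.5 makes the safety primary endpoints descriptive only.

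**The concern.** The measures named for GI tolerability do not isolate GI events. A child with a respiratory infection and a child with vomiting each add one to the any-TEAE numerator, and a child with both also adds one. COVID-19 cases must be recorded as adverse events (Protocol 10.1). Events that have nothing to do with iron therefore raise both arms and narrow the gap between them.

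The denominator does not match the objective either. The Safety Population is every randomised or assigned subject who was dosed (SAP 3.2.3). Up to 12 infants enter the ferric maltol arm with no counterpart on ferrous sulfate. If an interim analysis is run and is not significant, all later subjects are also assigned to ferric maltol (Protocol 12.1, SAP 4.1). For Hb, SAP 3.4.1 plans a separate analysis of randomised subjects only. No such analysis is stated for adverse events, and SAP 3.6.1 gives no age split for its tables.

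At stake is which number answers the GI half of a primary objective. The stated rule gives a diluted contrast between arms that are not fully randomised. The more relevant GI rows have no designated role.

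**Working it through.** **1. The plan's own figure.** The documents give no rate, difference or power for GI tolerability. The only power figure is for Hb in the ferric maltol arm: at least 80% with n = 49, SD 1.2 g/dL and mean change 0.5 g/dL. It reproduces: 0.5/(1.2/√49) = 2.917; 2.917 − 1.960 = 0.957; Φ(0.957) = 83.1%. The exact t calculation gives 81.5%. This figure does not bear on GI tolerability.

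**2. Objective against analysis.**

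| | Objective (SAP 2.1.1) | Stated comparison (SAP 3.6, Protocol 12.2.1) | GI rows (SAP 3.6.1) |
|---|---|---|---|
| Outcome | Safety and GI tolerability | All-cause TEAE, TESAE, discontinuation TEAE | One system organ class among all |
| Children compared | Ages 2–17 | Whole Safety Population | Whole Safety Population |
| Designated as GI measure | – | Yes, by the sentence itself | No |
| Difference with CI | – | Not stated | Not stated |

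**3. Dilution.** Let g be the GI TEAE risk in an arm and b the risk of any non-GI TEAE. Assume b is the same in both arms and independent of GI events. Then

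any-TEAE risk = 1 − (1 − b)(1 − g),

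so any-TEAE difference = (1 − b) × GI difference.

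The inputs g and b are assumptions. The 49 per arm is from SAP 2.2.2. The 95% half-width is 1.96 × √[p₁(1 − p₁)/49 + p₂(1 − p₂)/49].

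With assumed GI risks of 20% (ferric maltol) and 40% (ferrous sulfate):

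| Measure | Ferric maltol | Ferrous sulfate | Difference | Half-width |
|---|---|---|---|---|
| GI TEAE | 20% | 40% | 20 points | 17.7 |
| Any TEAE, b = 30% | 44% | 58% | 14 points | 19.6 |
| Any TEAE, b = 50% | 60% | 70% | 10 points | 18.8 |
| Any TEAE, b = 70% | 76% | 82% | 6 points | 16.1 |

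With assumed GI risks of 10% and 30%, the differences are again 20, 14, 10 and 6 points, with half-widths 15.3, 19.5, 19.3 and 16.9. The contrast shrinks while its imprecision stays about the same. The calculation covers the any-TEAE measure only. The documents give no rates from which to work the other two.

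**4. Population.** At full recruitment, with everyone dosed, the ferric maltol arm has 49 randomised children and up to 12 infants. If their event risks are p and q, the arm's rate is (49p + 12q)/61 = p + 0.197 × (q − p). Each 10-point gap between infants and older children therefore moves the ferric maltol rate by about 2 points, in a direction the documents do not settle. Subjects assigned after an interim would add to this, by a number that depends on when the interim falls.

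**The case against.** The strongest reply is that the GI analysis is already planned. The system organ class tables give GI-disorders incidence by arm for all TEAEs, drug-related TEAEs and TEAEs leading to discontinuation. In those tables a child with both tonsillitis and vomiting appears in both rows, and event counts are given as well. This stands. A reader might infer that the trial cannot answer its GI question, or that any use of the GI row would be a post-hoc choice. The documents support neither. The rows are pre-specified, and only their designation, restriction and interval are left open.

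Three further points also stand:
- **No planned inference is lost.** The objective is to compare, and no GI difference is hypothesised, powered or tested. The half-widths above show precision only.
- **The dilution cannot be sized from the documents.** It is tempting to take the 54.1% TEAE rate in the earlier paediatric study (Protocol 5.4.3) as the background. That figure mixes GI and non-GI events, covers a 10-day treatment period and has no ferrous sulfate arm, so it does not estimate b.
- **The intolerance record is not wholly unused.** It may appear among the reasons for early discontinuation in SAP 3.3.1. It is simply not linked to the tolerability endpoint.

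The reply leaves two things untouched. The sentence that says how GI tolerability will be compared names only all-cause measures, and its denominator includes children outside the randomised comparison.

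**Conclusion.** The point holds as a mismatch between a primary objective and the measures stated for it. GI tolerability at ages 2 to 17 is to be compared by all-cause rates in a population that also contains subjects who could only receive ferric maltol. Under independence and equal background rates, the any-TEAE difference is (1 − b) times the GI difference: 14, 10 or 6 points in place of an assumed 20 for b of 30%, 50% or 70%. The direction holds for any b above zero under those assumptions. The true size is unknown. The effect is on estimation and interpretation of a descriptive endpoint. Because undiluted GI rows will be produced anyway, this is a low-cost improvement and not a failure of the trial.

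**What to change.** In Protocol 6.3 and 12.2.1 and SAP 2.3.1 and 3.6, designate two GI tolerability measures in randomised children aged 2 to 17:

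1. Subjects with at least one TEAE in the MedDRA Gastrointestinal disorders class.
2. Subjects with such a TEAE leading to study drug discontinuation.

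Present each by arm with the risk difference and 95% CI. Report recorded discontinuation for intolerance alongside. Keep the all-cause TEAE, TESAE and discontinuation rates as the safety measures.

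The cost is wording in both documents and one table from data already collected and coded. No new data are needed.

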6 STUDY OBJECTIVES AND ENDPOINTS

6.1 PRIMARY OBJECTIVES:

- To compare the safety and gastrointestinal tolerability of ferric maltol oral suspension and ferrous sulfate oral liquid in children and adolescents aged 2 years to 17 years and assess the safety and tolerability of ferric maltol oral suspension in children 1 month to less than 2 years, in the treatment of iron deficiency anaemia during the 12 weeks treatment period.
- 2. To assess the effect on haemoglobin in children and adolescents aged 1 month to 17 years after twice daily ferric maltol oral suspension administration for 12 weeks

6.2 SECONDARY OBJECTIVES:

- 1. To assess the pharmacokinetics (PK) in children and adolescents aged 2 to 17 years after a single dose of ferric maltol oral suspension on Visit 2 (PK Day 1), and after twice daily administration for at least 6 days, on Visit 3 (PK Day 2), after a single morning dose, through measurement of serum iron, corrected serum iron, transferrin saturation (TSAT) and plasma maltol and maltol glucuronide
- 2. To assess the effect on iron markers in children and adolescents aged 1 month to 17 years after twice daily ferric maltol oral suspension administration for 12 weeks
- 3. To assess the PK, in children aged 1 month to less than 2 years of age after a single dose of ferric maltol oral suspension (Pre-assignment PK visit) and after twice daily administration for at least 6 days, on Visit 3 (PK Day 2), after a single morning dose, through measurement of serum iron, corrected serum iron, transferrin saturation (TSAT) (PK Day 2 only), plasma (PK Day 2 only) and urine concentration of maltol and maltol glucuronide
- 4. To assess the effect, in children aged 1 month to less than 2 years of age after twice daily administration for at least 6 days, on Visit 3 (PK Day 2) after a single morning dose, on serum transferrin, total and unsaturated iron binding capacity (TIBC, UIBC)
- 5. To assess the effect, in children aged 2 to 17 after a single dose of ferric maltol suspension Visit 2 (PK Day 1), and after twice daily administration for at least 6 days, on Visit 3 (PK Day 2) after a single morning dose, on serum transferrin, total and unsaturated iron binding capacity (TIBC, UIBC).
- 6. To compare the palatability from age-appropriate scoring system of ferric maltol oral suspension and ferrous sulfate oral liquid

CONFIDENTIAL Page 40 of 80

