12 STATISTICAL CONSIDERATIONS

12.1 POWER CALCULATIONS

The study will be analysed by descriptive statistics only. As such, there is no formal power calculation.

The aim is to recruit up to 49 subjects in each treatment group in the 2-17 years cohort. At least 12 subjects in each age group (i.e. 36 subjects in total) will be included in the PK model in the ferric maltol oral suspension group. A sample size of 49 in the Ferric Maltol group provides at least 80% power to demonstrate that the lower bound of the 95% confidence interval for increase in Hb at 12 weeks, compared with baseline, is above zero. This assumes that the SD of the change from baseline is 1.2 g/dL or lower and the true mean change is at least 0.5 g/dL.

Every effort will be made to recruit up to 12 subjects in the under 2's age group but in case of reasons of feasibility it cannot be completed, then the study may be completed without that cohort.

If less than 91 subjects in total have been randomized when 32 ferric maltol subjects have completed, then an interim analysis of the primary effectiveness endpoint (change in Hb concentration from baseline to Week 12) will be conducted. Less than 91 subjects recruited would indicate that the study will not complete in the near future.

The interim analysis will test for significance of the increase in Hb in the ferric maltol arm (from Baseline to Week 12). If significant, the study will stop recruitment. If not significant, the study will continue (all subjects will be assigned to ferric maltol) until 54 subjects have been recruited in the ferric maltol arm.

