2.1.2 Secondary Objectives

- To assess the pharmacokinetics (PK) in children and adolescents aged 2 to 17 years
 after a single dose of ferric maltol oral suspension on Visit 2 (PK Day 1), and after twice
 daily administration for at least 6 days, on Visit 3 (PK Day 2) after a single morning dose
 through measurement of serum iron, corrected serum iron, transferrin saturation (TSAT)
 and plasma maltol and maltol glucuronide.
- To assess the effect on iron markers in children and adolescents aged 1 month to 17 years after twice daily ferric maltol oral suspension administration for 12 weeks.
- To assess the PK, in children aged 1 month to less than 2 years of age after a single dose of ferric maltol oral suspension (Pre-assignment PK visit) and after twice daily administration for at least 6 days, on Visit 3 (PK Day 2) after a single morning dose, through measurement of serum iron, corrected serum iron, TSAT (PK Day 2 only), plasma (PK Day 2 only) and urine concentration of maltol and maltol glucuronide.
- To assess the effect in children aged 1 month to less than 2 years of age after twice daily administration for at least 6 days on Visit 3 (PK Day 2) after a single morning dose, on serum transferrin, total and unsaturated iron binding capacity (TIBC, UIBC).
- To assess the effect, in children aged 2 to 17 years after a single dose of ferric maltol suspension Visit 2 (PK Day 1), and after twice daily administration for at least 6 days, on Visit 3 (PK Day 2) after a single morning dose, on serum transferrin, TIBC and UIBC.
- To compare the palatability from age-appropriate scoring system of ferric maltol oral suspension and ferrous sulfate oral liquid.

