3.1.5 Hypothesis Testing

Hypothesis testing will be performed for the interim analysis to test the hypothesis that the ferric maltol Hb change from baseline to Week 12 is > 0. If an interim analysis is conducted, a Pocock spending function will be used; the interim analysis will be based on a (100-3.45)% two sided confidence interval.

The efficacy primary endpoint will also involve hypothesis testing. If no interim analysis is conducted the hypothesis testing will be based on a 95% two-sided confidence interval. If the study does not stop after the interim analysis, the final analysis will be based on a (100-2.57)% two sided confidence interval.

The study safety primary endpoints will be analysed by descriptive statistics only. The secondary endpoints will be analysed by descriptive statistics only. Thus, no formal testing strategy or adjustments of the Type I error will be employed for the evaluation of secondary endpoints.

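### Primary objective 1 compares safety between arms at ages 2–17, but the plan gives per-arm incidences only, with no between-arm difference or interval and no restriction to randomised subjects

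*SAP*

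**What the plan says.** Protocol 6.1 has two primary aims. For the randomised age range, 2–17, the first reads: "To compare the safety and gastrointestinal tolerability of ferric maltol oral suspension and ferrous sulfate oral liquid in children and adolescents". SAP 2.1.1 repeats it. For infants under 2 years the same objective is only to assess.

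The planned method is in Protocol 12.2.1 and SAP 3.6. The latter states that "Safety and gastrointestinal tolerability will be compared between ferric maltol oral suspension and ferrous sulfate oral liquid via the incidence of TEAEs". It names two further measures, serious events and events that made a subject stop treatment. All three use a simple proportion: "estimated as the number of subjects with at least one event divided by the number of subjects in the Safety Population". SAP 3.6.1 describes the tables: "An overview of AEs will be provided including counts and percentages of subjects (and event counts) with the following". The listed categories include maximum severity and relatedness, and each is repeated by system organ class and preferred term.

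The inferential status is declared. SAP 3.1.5: "The study safety primary endpoints will be analysed by descriptive statistics only". Protocol 12.1 applies this to the whole trial and draws the consequence for sample size: "The study will be analysed by descriptive statistics only. As such, there is no formal power calculation".

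Palatability is also comparative: "To compare the palatability from age-appropriate scoring system of ferric maltol oral suspension and ferrous sulfate oral liquid" (SAP 2.1.2). For secondary endpoints, Protocol 12.2.2 and SAP 3.4.2 plan per-group summaries with 95% intervals where applicable.

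The SAP 3.2.3 Safety Population takes in assigned as well as randomised subjects.

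**The concern.** The Hb objective concerns ferric maltol alone. Primary objective 1 is the primary objective that needs the randomised ferrous sulfate arm, yet the analysis stops one step short of a comparison: two proportions, with no difference and no statement of how precisely the difference is known. A reader shown a numerically lower rate may take it as better tolerability, and a reader shown equal rates may take them as similarity. The planned output gives no guard against either.

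The second part concerns who is compared. SAP 3.4.1 plans a separate Hb analysis of randomised subjects only; safety has no counterpart, and SAP 3.6.1 plans no age split of the adverse event tables. Subjects with no concurrent randomised comparator can therefore shift the ferric maltol percentage.

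**Working it through.** **The plan's own figure.** The only power statement (Protocol 12.1, SAP 2.2.4) is for the within-arm Hb change: n = 49, mean 0.5 g/dL, SD 1.2 g/dL, two-sided 95% interval above zero. Noncentrality = 0.5 / (1.2/√49) = 2.917. Power is 81.5% (noncentral t, 48 df) or 83.1% (normal approximation), so the stated figure of at least 80% reproduces. It is a before/after figure for one arm and says nothing about the safety comparison, for which no precision or margin is stated.

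**What is planned for each endpoint.**

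| Endpoint | Per-arm summary | Interval | Between-arm difference |
|---|---|---|---|
| Hb change (primary) | yes | yes | only through the model's sample code, SAP Appendix C |
| Three safety endpoints (primary) | yes | no | no |
| Palatability (secondary) | yes | per group, where applicable | no |

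**What the missing interval would show.** Inputs: 49 per arm (SAP 2.2.2). Event counts are assumptions, because the documents give no 12-week rates by arm. The one paediatric rate, 20/37 (54.1%) in the earlier PK study (Protocol 5.4.3), comes from a 10-day regimen.

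Newcombe interval, with d = p1 − p2 and Wilson limits (l, u) for each arm:
- lower = d − √[(p1 − l1)² + (u2 − p2)²]
- upper = d + √[(u1 − p1)² + (p2 − l2)²]

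For 20/49 versus 25/49, the Wilson limits are 0.282–0.548 and 0.375–0.644, and d = −0.102.
- lower = −0.102 − √(0.126² + 0.134²) = −0.286
- upper = −0.102 + √(0.139² + 0.136²) = +0.092

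| Assumed counts (ferric maltol vs ferrous sulfate) | Difference, points | 95% CI |
|---|---|---|
| 20/49 vs 25/49 | −10.2 | −28.6 to +9.2 |
| 20/49 vs 20/49 | 0 | −18.8 to +18.8 |
| 10/49 vs 20/49 | −20.4 | −37.0 to −2.1 |
| 13/32 vs 16/32 | −9.4 | −31.6 to +14.3 |

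The last row assumes equal arms of 32 after an early stop. The trigger is 32 ferric maltol completers with fewer than 91 randomised, so up to 90 children (about 45 per arm) could already be in the trial; 32 is a low case.

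**Chance gaps when true rates are equal** (two independent binomials, 49 per arm):

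| True rate | Gap ≥ 10 points | Gap ≥ 20 points |
|---|---|---|
| 10% | 13% | 0.2% |
| 20% | 25% | 1.6% |
| 30% | 32% | 3.6% |
| 50% | 36% | 5.4% |

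A gap of about 10 points is ordinary noise; one of 20 points is uncommon.

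**What similarity would need.** Assume a 50% rate in both arms, one-sided 2.5% and 80% power. Then n per arm = (1.960 + 0.842)² × 2 × 0.5 × 0.5 / margin². This gives 393 for a 10-point margin, 175 for 15 and 99 for 20. The margins are illustrative.

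**Effect of adding infants.** Take an assumed 20/49 (40.8%) among randomised children on ferric maltol. Adding 12 infants gives from 20/61 (32.8%) if none has an event to 32/61 (52.5%) if all do. These are outer bounds, not forecasts, but the ferrous sulfate column has no matching subjects.

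**The case against.** The strongest reply is that the plan is open about being descriptive. Both documents say so, and Protocol 12.2.1 and SAP 3.6 define what the comparison consists of. That stands: nothing is hidden, and the fault is a mismatch between an objective to compare and a plan without a comparative estimate. It does not remove the point, because a difference with an interval is itself descriptive estimation and leaves SAP 3.1.5 intact.

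A reader might infer that the safety output is just two percentages. The documents do not support this: SAP 3.6.1 adds event counts, severity, relatedness and tables by organ class, so gastrointestinal disorders will be visible. A reader might also infer that the trial cannot say whether the products differ. That is too strong, since counts and denominators are tabulated and 10/49 versus 20/49 would exclude zero. Such a back-calculation would, however, inherit whatever non-randomised subjects sit in the ferric maltol column.

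A reader might infer that palatability has no interval at all. SAP 3.4.2 contradicts this: a per-group interval for the mean is planned where applicable, and Protocol 10.8.4 converts the faces to scores of 1 to 5. Only the between-arm difference is missing.

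Finally, stratifying by age group and sex would leave four strata averaging about 12 per arm (49/4), which is sparse for serious events and discontinuations. Using the strata is a choice; leaving them out is not a defect.

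**Conclusion.** The point holds in this form: a comparative primary objective has no prespecified between-arm estimate or interval, and SAP 3.6 does not confine the comparison to the randomised population. It is an inexpensive improvement that should be made, not an error that invalidates the trial.

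Under the assumed counts, a 10-point difference at 49 per arm has an interval running about 19 points either side. Equal rates of 20/49 are compatible with a true difference of up to about 19 points in either direction, and only observed gaps of roughly 20 points begin to exclude zero. These sizes rest on illustrative event counts and on full recruitment of 49 per arm.

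A reader might expect the added interval to let the trial conclude that the products are alike. It would not: that limit comes from the sample size, and the interval only makes it visible.

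**What to change.** 1. In SAP 3.6, for randomised subjects aged 2–17 in the Safety Population, add the ferric maltol minus ferrous sulfate risk difference with 95% CI (Newcombe or Miettinen-Nurminen). Cover four endpoints: any TEAE, any TESAE, any TEAE leading to discontinuation of study drug, and any TEAE in the gastrointestinal disorders organ class. The last is needed because the objective names gastrointestinal tolerability. Stratification by age group and sex can be optional where cells allow.
2. Present infants and any subjects assigned after the interim separately from this comparison.
3. Label the intervals as estimation without hypothesis tests, and state that equal rates will not be described as similarity unless the interval supports it.
4. In SAP 3.4.2, add the between-arm difference in hedonic score with 95% CI at Visits 2 and 4, beside the per-group intervals.

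The alternative is to reword the comparative objectives to describe rather than compare.

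Cost: SAP wording and a few table columns, with no new data and no alpha spent. The downside is that the intervals will be wide and will show the low precision plainly.
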